8. Self-Monitoring Blood Glucose (SMBG) device to be provided at Visit 2 to patients who need wash-out of an OAD or at Visit 4 to patients who do not need washout. Patients should be instructed to monitor fasting blood glucose at least once daily before breakfast (if possible, it is recommended to monitor fasting blood glucose in preprandial state and before bedtime) and at any time the patient is symptomatic related to hypoglycaemia or hyperglycaemia through the entire study period (i.e., after providing the SMBG device until the end of follow-up). In addition, in 3 consecutive days in the week before each scheduled visit, patients will be requested to monitor fasting blood glucose at preprandial state (i.e., before breakfast, lunch and dinner), before bedtime and at any time when the patient is symptomatic. Patients are requested to maintain a diary with daily recordings of glucose values measured by SMBG and of insulin dose through the entire study period.
9. At all the visits which are marked on the [flow chart](#), the respective kit number has to be allocated to the patient via IRT.
10. Only includes liver transaminases (i.e. AST and ALT), ALP, serum creatinine, TSH and urinalysis.
11. No need to be collected in fasted state.
12. In case of early discontinuation from treatment, the end of treatment (EOT) visit has to be performed within 7 days of the last dose of the study drugs. And the follow up (F-up) visit has to be performed after 7 days of the EOT (with +7 days allowance).
13. Patients who are pretreated with insulin alone skip the HbA_{1c} measurement at Visit 4.
14. For patients who completed the trial without any persisting adverse event at EOT, a follow-up visit can be performed as a phone visit (only information on SMBG log, adverse events, and concomitant therapies are to be obtained). For patients who completed the trial with persisting adverse event(s) at EOT and patients who early discontinued the 52 weeks treatment period, an EOT and a follow-up visit (at the follow up-visit, physical examination, vital signs, and safety lab and should be performed additionally) should be performed at clinic visits.
- 15.
16. Only blood sampling for haematology and urinalysis will be performed.
17. C-peptide will be measured at Visit 2 in patients who need wash-out of an OAD or Visit 4 in patients who do not need wash-out.

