5.3.3 Safety laboratory parameters

All safety laboratory samples (except at Visit 1) will be collected after a full overnight fast (nothing to eat or drink except water for at least 10 hours) and before investigational drug is taken as described in the [flow chart](#) and [Section 6](#). The blood sample at Visit 1 (screening visit) can be taken with the patient in a fasted or non-fasted state.

All parameters that will be determined during the trial conduct are listed in [Tables 5.3.3: 1](#) and [5.3.3: 2](#). The analysis will be performed by a central laboratory. The respective reference range and details about sample handling and shipment will be provided in the ISF (Lab Manual).

Reduced lab panels are planned for the following visits (For details, see the [flow chart](#)):

- For the screening Visit 1, laboratory only includes liver transaminases (i.e., AST and ALT), alkaline phosphatase, serum creatinine, thyroid stimulation hormone (TSH) , anti-GAD antibody, Ant-IA-2 antibody, FPG, HbA_{1c} and urinalysis.
- C-peptide will be measured at Visit 2 in patients who need washout an OAD or Visit 4 in patients who do not need washout period.
- Free fatty acid (FFA) and Blood ketone bodies will be measured at selected visits. For the details, see the [flow chart](#).
- Bone markers; iPTH (intact parathyroid hormone), 25OH Vitamin D, NTx in urine: planned at Visits 5, 10 and EOT.
- Hematology and urinalysis will also be measured at Visit 6, 7, 9 11, 12, 14, 15, 17 and 18.

Table 5.3.3: 1

Safety laboratory parameters – whole blood, serum or plasma

Haematology

- Haematocrit
- Haemoglobin
 - Reticulocyte count (reflex test if Hb outside normal range)
- Red blood cells (RBC)/Erythrocytes
- White blood cell (WBC)/Leukocytes
- Platelet count/Thrombocytes
- Differential automatic (relative and absolute count):
Neutrophils, eosinophils, basophils, monocytes, lymphocytes

Clinical chemistry

- Albumin
- ALP
- γ -GT (gamma-glutamyl transferase)
- ALT (alanine aminotransaminase, SGPT)
- AST (aspartate aminotransaminase, SGOT)
- Bicarbonate
- Bilirubin total, fractionated if increased
- C-peptide
- Calcium
- Chloride
- Creatinine
- Creatinine kinase (CK)
- hs troponin T (reflex tests if CK is elevated)
- Lactate dehydrogenase (LDH)
- Lipase
- Magnesium
- Phosphate
- Potassium
- Protein total
- Sodium
- TSH (only at Visit 1)
- Urea (BUN)
- Uric acid
- Cholesterol (total)
- HDL cholesterol
- Calculated LDL cholesterol

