- Triglycerides (reflex test for direct measurement of LDL cholesterol triggered if triglycerides are >400 mg/dL or 4.52 mmol/L)

Table 5.3.3: 1 Safety laboratory parameters – whole blood, serum or plasma (continued)

Bone Marker (only at selected visits)

- iPTH
- 25OH Vitamin D
- NTx in Urine

FFA and Ketone bodies (only at selected visits)

- Total ketone body
- Acetoacetic acid
- 3-hydroxybutyric acid
- Free fatty acid (FFA)

Other

- Anti-GAD antibody
- Anti-IA-2 antibody

Table 5.3.3: 2 Safety laboratory parameters – urine

Urinalysis	Microscopic analysis
Semi quantitative (dipstick)	Will be performed as reflex test if any of the semi quantitative tests/dipsticks are abnormal:

• Nitrite*• Protein• Ketone• Urine pH• Leukocyte esterase (for WBC)*	
• Urine RBC/Erythrocyte• Urine WBC/Leukocytes• Urine sediment microscopic examination• Urine culture (including antibiogram test):
- reflex test triggered by positive leukocyte esterase (for WBC) and/or nitrite in the semi-quantitative test/dipstick
Quantitative	

• Albumin• Creatinine	

* Nitrite and leukocyte esterase (for WBC) will be determined both locally on site (not recorded in eCRF) and via central lab. A positive result at site triggers the sampling of mid-stream urine for urine culture.

Albumin/creatinine ratio in spot urine will be calculated at the central lab.

Glomerular filtration rate:

The eGFR will be derived from serum creatinine values for Japanese equation:

$$\text{eGFR (mL/min/1.73m}^2\text{)} = 194 \times [\text{Screatinine (mg/dL)}]^{-1.094} \times [\text{age}]^{-0.287} \times [0.739 \text{ if patient is female}]$$

Renal function impairment will be classified in the following way:

- No renal function impairment: eGFR ≥ 90 mL/min/1.73m²;
- Mild renal function impairment: eGFR 60 to < 90 mL/min/1.73m²;
- Moderate renal function impairment: eGFR 30 to < 60 mL/min/1.73m²;
- Severe renal function impairment: eGFR < 30 mL/min/1.73m².

These classes of renal impairment will be the basis for stratification of subgroup analysis.

Pregnancy testing:

Pregnancy testing (urine) will be performed in female patients of child bearing potential only according to the time points indicated in the [flow chart](#).

Criteria for hypoglycaemic events:

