#### Safety and other variables

Missing safety data will not be replaced, but an analysis of the changes from baseline to the last available value under treatment and the minimum and maximum post baseline will be determined for quantitative safety laboratory variables.

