For the analysis of eGFR and for the covariates in the statistical modelling the values calculated from the above formula using the serum creatinine values from the central laboratory will be used, not the eGFR values provided by the central laboratory. For the assignment of IPVs based on renal function the central laboratory values will be used.

To support analysis of renal function, eGFR throughout the trial will be categorised according to the following eGFR staging.

Table 7.8.2: 1 eGFR staging (by Japanese formula)

Stage	eGFR [mL/min/1.73m^2]	Description
1	$\geq 90$	Normal renal function
2	60 to $< 90$	Mild renal impairment
3	30 to $< 60$	Moderate renal impairment
4	$< 30$	Severe to end-stage renal impairment

Staging of the eCcr will be prepared with respect to the following categorisation and a shift table will be supplied for eCcr as well.

Table 7.8.2: 2 Cockcroft-Gault eCcr staging

Stage	eCcr [mL/min]	Description
1	≥90	Normal renal function
2	60 to <90	Mild renal impairment
3	30 to <60	Moderate renal impairment
4	<30	Severe renal impairment and beyond (e.g., End-stage renal disease)

The analyses of laboratory data will be descriptive in nature and will be based on BI standards (see DM&SM: Display and Analysis of Laboratory Data) [4]

Baseline for safety laboratory parameters will be the last available measurement before the start of randomised study drug. Laboratory measurements taken up to 3 days after the last administration of randomised study drug will be considered as on-treatment.

Laboratory values will be compared to their reference ranges and frequency tables will be provided for the number of patients within and outside the reference range at baseline and the last measurement on treatment. Descriptive statistics will be provided by treatment group for baseline, on-treatment values and for changes from baseline. Frequency tables will summarise the number of patients with potentially clinically significant abnormalities as defined for the new XLAB macro. Summaries will also be presented for patients with elevated liver enzymes. A summary will also be created representing the number of patients per treatment group that experienced a doubling in creatinine on treatment compared to baseline that was out of the normal range.

Only patients with at least one available on-treatment value will be included in the analysis of an individual laboratory parameter. All individual data will be presented in listings.

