Urine creatinine does not have a reference range and is determined to calculate the albumin / creatinine ratio. Only the albumin / creatinine ratio will be analysed as for urine creatinine no normalised values can be derived. In cases where urine albumin values are reported to be BLQ (e.g. <3 mg/L) the albumin / creatinine ratio is determined as missing and will not be replaced by estimated values. Four additional summaries will be presented for the descriptive statistics of urine albumin/creatinine ratio by baseline value (normal <30mg/g, microalbuminurea 30-<300 mg/g and macroalbuminurea  $\geq$ 300 mg/g) and transitions from baseline based on the aforementioned categories. Similar analyses will be provided for urine albumin with the following categories (<20mg/L; 20-<200mg/L;  $\geq$ 200mg/L).

A shift table from baseline to last value on treatment for eGFR (Japanese formula) will be provided in Section 15 and a shift table from baseline to last value on treatment for eCcr (Cockcroft-Gault) will be provided in Section 16.1.9.2.

General laboratory evaluation will also be provided for bone markers.

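### Setting the albumin/creatinine ratio to missing for every BLQ urine albumin removes known-normal samples from the ratio category and transition tables (low priority)

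*SAP*

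**What the plan says.** SAP Section 7.8.2 analyses the urine albumin/creatinine ratio but not urine creatinine itself, which is measured only to form the ratio. For a BLQ albumin, with under 3 mg/L given as an example, "the albumin / creatinine ratio is determined as missing and will not be replaced by estimated values". The next sentence plans summaries by baseline category (normal below 30 mg/g, 30 to below 300, and 300 or more) and "transitions from baseline based on the aforementioned categories". No condition on creatinine is attached, and the category tables are not exempted. A parallel analysis of urine albumin in mg/L follows, with a lowest category below 20 mg/L.

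Three other rules bear on the result:

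- **Baseline (SAP 7.8.2).** "Baseline for safety laboratory parameters will be the last available measurement before the start of randomised study drug".
- **Inclusion (SAP 7.8.2).** "Only patients with at least one available on-treatment value will be included in the analysis of an individual laboratory parameter".
- **Denominator (SAP Section 7).** Percentages in frequency tables use every patient in the set, with or without a value.

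SAP 6.6 also plans, for quantitative safety laboratory variables, an analysis of "changes from baseline to the last available value under treatment". Protocol 5.3.3 adds: "Albumin/creatinine ratio in spot urine will be calculated at the central lab".

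**The concern.** A BLQ albumin is informative. With measured creatinine it gives a ceiling for the ratio, and in nearly every sample that ceiling lies inside the normal category. Coding the ratio as missing discards a known category, and only ever for the lowest albumin values. The patients lost from a transition table are mostly those who are normal at both times, so the remaining baseline-normal group looks more prone to progress than it is.

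There is a second, conditional route. If a ratio set to missing does not count as available, an earlier quantifiable sample takes its place at baseline or at the end of treatment. Patients who are BLQ at every on-treatment visit then leave the analysis. At stake is how the albuminuria tables read in the safety section of the report.

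**Working it through.** The plan states no figure that depends on this rule, so there is nothing to reproduce first.

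**1. The bound.** If albumin is below L (mg/L) and creatinine is C (g/L), the ratio is below L/C. It is certainly below 30 mg/g when C ≥ L/30. With L = 3: 3/30 = 0.1 g/L, or 10 mg/dL. The ceiling is 15 mg/g at 20 mg/dL, 6 at 50 mg/dL and 3 at 100 mg/dL. Below 10 mg/dL the category is uncertain (up to 60 mg/g at 5 mg/dL). The 3 mg/L is only an example; at 1, 5 or 10 mg/L the creatinine threshold would be 3.3, 16.7 or 33.3 mg/dL.

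**2. Patients lost from a fixed-visit table.** The BLQ share b is not in the documents. Take b = 5% to 30% at each of two times, with 89 patients per arm (Protocol 7.7). If the same patients are BLQ both times, the loss is 89 × b = 4.5 to 26.7. If BLQ status is independent, it is 89 × (1 − (1 − b)²) = 8.7 to 45.4.

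**3. Sampling schedule.** Protocol 5.3.3: "Hematology and urinalysis will also be measured at Visit 6, 7, 9 11, 12, 14, 15, 17 and 18", which is nine visits. The full panel is taken to fall at the remaining Visits 8, 10, 13, 16 and 19. This is by elimination, because the flow-chart row is broken in the available text. Total: 14 on-treatment samples. Before treatment there are Visits 4 and 5, plus Visit 1, whose reduced panel "Only includes liver transaminases (i.e. AST and ALT), ALP, serum creatinine, TSH and urinalysis". Total: 3.

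**4. Simulation.** All distributional inputs are assumptions: log-normal values, no drug effect, no dropout, limit 3 mg/L. There are nine scenarios:

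- Albumin median 6, 12 or 20 mg/L, independent of creatinine (median 0.9 g/L, log-SD 0.5).
- Ratio median 6.7, 13.3 or 22.2 mg/g, independent of creatinine (median 0.9 g/L with log-SD 0.5, or dilute urine at 0.6 g/L with log-SD 0.6).

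Each was run with within-patient creatinine correlation 0 and 0.5. The log-SD and correlation below refer to albumin or the ratio. Excess progression is in percentage points.

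| Log-SD, correlation | Scenarios | Baseline-normal, last available | Baseline-normal, single visit | All patients |
|---|---|---|---|---|
| 1.3, 0.75 | all nine | 1.0 to 3.3 | 4.3 to 9.9 | +0.1 to +0.5 (last available); −0.1 to −0.8 (single visit) |
| 0.9, 0.75 | albumin medians only | 0.2 to 0.7 | 1.1 to 2.6 | about 0.04 or less |
| 1.3, 0.5 | albumin medians only | 1.6 to 3.0 | 5.1 to 8.3 | up to about +1.1 / −1.1 |
| 1.3, 0.5 | all nine | 1.6 to 5.1 | 5.1 to 11.7 | up to +1.6 / −2.3 |

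With two pre-treatment samples, the first row's last-available excess becomes 1.5 to 4.1. The last row shows that these ranges illustrate the size and do not bound it.

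**5. One case in detail** (albumin median 12 mg/L, log-SD 1.3, correlation 0.75, creatinine correlation 0). BLQ is 14.2% of samples. True progression among baseline-normal patients is 15.9%. As written it becomes 17.6% (last available) or 21.8% (single visit). With the fix it is 15.9%. For all patients the truth is 11.4%, and the error is +0.17 or −0.20 points.

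The single-visit figures show the mechanism. Truly baseline-normal patients are 11.4/0.159 = 71.7% of the total; those kept are 11.2/0.218 = 51.4%. Normal-to-normal patients fall from 71.7 − 11.4 = 60.3% to 51.4 − 11.2 = 40.2%, a loss of about one third. Progressors lose only 0.20/11.4, about 2%.

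**6. Sensitivity to the limit** (log-SD 1.3, correlation 0.75, baseline-normal denominator). At 1.5 mg/L the excess is 0.2 to 1.1 (last available) and 1.4 to 4.2 (single visit). At 5 mg/L it is 3.0 to 7.4 and 9.1 to 17.6, with the all-patients effect between −2.1 and +0.9.

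**7. With the fix** (log-SD 1.3, correlation 0.75, limit 3 mg/L), 99.4% to 100% of BLQ samples can be classed, and progression is within 0.02 points of the truth in both table types.

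**The case against.** The best case for leaving the plan alone has four parts.

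- **Consequence.** Albuminuria is neither the primary nor the secondary endpoint, and the renal event of special interest is defined on serum creatinine. The tables are descriptive and the rule is the same in every arm. This stands and sets the priority.
- **Size and direction.** Spread, correlation and BLQ frequency are all unknown, and with a smaller spread the effect nearly vanishes. On the all-patients denominator of SAP Section 7 the sign flips with the timepoint, which the SAP does not name for transitions. This also stands: no single figure or direction can be claimed for the trial.
- **Other sources.** The parallel urine albumin table can hold a value under 3 mg/L in its lowest category, and individual data are listed. This is a partial offset: the SAP does not say how BLQ values enter that table, and it is not creatinine-adjusted. The cited sponsor laboratory guidance was not seen and may settle BLQ handling, denominators and what counts as available.
- **Carry-back.** Replacement by an earlier sample requires that a BLQ ratio is not available, which neither document says. The SAP 6.6 wording on last available values concerns changes in quantitative variables, not category transitions. The carry-back is therefore a possibility only.

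A reader might go further and infer that the rule biases empagliflozin against placebo. The protocol describes a diuretic action, and diluted urine would push more albumin values below the limit without changing the ratio. An assumed dilution of 20% to 35% gave a spurious difference of 0.2 to 0.6 points (last available) or 1.0 to 2.4 points (single visit). The documents give no dilution figure, so this is a mechanism, not a demonstrated distortion. It does support counting BLQ samples by arm.

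**Conclusion.** The point holds as a low-priority improvement. As written, the rule discards a category that the measured creatinine already establishes, and it does so only at the low end. That much needs no assumption beyond an assay limit.

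Among baseline-normal patients with values, progression tends to be overstated. With a 3 mg/L limit, log-SD 0.9 to 1.3 and correlation 0.5 to 0.75, the excess is about 0.2 to 3–4 points (last available) or about 1 to 10 points (single visit). On the all-patients denominator the effect is about 0 to 1.1 points in either direction. Low correlation with dilute urine takes these to about 5, about 12, and between +1.6 and −2.3 points. Every input except the example limit and the visit schedule is assumed.

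The documents do not support saying that the tables will mislead by a given amount, that the error always runs one way, or that the arms are affected differently. The HbA1c analysis is untouched.

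**What to change.** Add one sentence to SAP 7.8.2. In the ratio category and transition tables, a sample with BLQ albumin is classed as normal (below 30 mg/g) when the assay limit divided by urine creatinine is at or below 30 mg/g. It counts as an available category when the baseline and on-treatment values are chosen, and otherwise stays missing. The rule should use the laboratory's actual limit. Report the number of BLQ samples by arm and visit. The continuous ratio can stay missing as planned, so no value is estimated.

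The same edit could name the on-treatment timepoint and the denominator for the transition tables, or confirm that the sponsor's laboratory guidance does.

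Cost: one short derivation from data already collected. The category tables will contain more patients than the continuous summaries, so a footnote must explain the two Ns.

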### **7.8.3 Vital signs**

Other than the analysis of SBP and DBP as efficacy endpoints only descriptive statistics are planned for the summary of pulse rate (bpm), change from baseline in pulse rate over time up to week 52.

### **7.8.4 ECG**

12-lead ECG measurements will be taken at baseline (visit 5), visit 8, visit 10, visit 13, visit 16 and visit 19. ECG-findings before first intake of trial drug will be considered as baseline condition. Any clinically significant new findings in the ECG measurement after the first screening ECG were to be reported by the investigator as AEs and will be analysed as planned in [Section 7.8.1](#).

### **7.8.5 Creatinine and eGFR time curve analysis**

Descriptive statistics will be created for creatinine and eGFR values over time by treatment and presented in tables. Descriptive statistics for eCcr will be presented in Section 16.1.9.2. These data will be used to create plots of the parameters over time. Subgroups tables of these descriptive statistics over time will also be presented for age subgroups.

### **7.8.6 Lipid parameter and FFA analyses**

Lipid parameters and FFA will be analysed using descriptive statistics and MMRM modelling. Descriptive statistics will be shown over time for the treated set (LOCF-IR and OC-IR) including change from baseline and percent change from baseline. For each lipid parameter and FFA, separate MMRM models will be fitted on the treated set (OC-IR) for both change from baseline at week 52 and percentage change from baseline at week 52 as dependent variables. The MMRM models will include ‘baseline lipid’ (only for lipid parameters), ‘baseline FFA’ (only for FFA) and ‘baseline HbA1c’ as continuous covariates and ‘baseline eGFR (Japanese formula)’, ‘type of insulin therapies’, ‘treatment’, ‘visit’ and ‘treatment by visit interaction’ as fixed effects.

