7.3.1 Primary endpoint analyses

The primary analysis will be performed on the FAS with missing data imputed using a last observation carried forward (LOCF) approach as described in [Section 7.4](#).

The primary endpoint will be analysed using an ANCOVA. The model includes 'treatment', 'baseline renal function' and 'type of insulin therapies' as a fixed effect, and baseline HbA_{1c} as a covariate as follows:

Change from baseline in HbA_{1c} after 16 weeks = overall mean + baseline HbA_{1c} + treatment + baseline renal function + type of insulin therapies + random error

The random error is assumed to be normally distributed with mean 0 and variance σ^2 .

[Sensitivity analysis]

Sensitivity analyses of the primary endpoint will be performed as follows:

- The primary analysis as specified in [Section 7.3.1](#) will be repeated on the PPS (LOCF).
- The primary endpoint will be analysed on the FAS (observed case, OC) using a restricted maximum likelihood (REML)-based mixed model repeated measures (MMRM). The model includes 'treatment', 'baseline renal function', 'type of insulin therapies', 'visit', 'treatment by visit interaction' and 'baseline HbA_{1c} by visit interaction' as a fixed effect, and baseline HbA_{1c} as a covariate as follows:

Change from baseline in HbA_{1c} at each on-treatment visit = overall mean + baseline HbA_{1c} + treatment + baseline renal function + type of insulin therapies + visit + treatment by visit interaction + baseline HbA_{1c} by visit interaction + random error

For each patient, the error terms from the on-treatment visits represent the within-patient variability, and are assumed to follow a multivariate normal distribution with an unstructured covariance matrix.

If this unstructured covariance structure fails to converge, the following structures will be tested: compound symmetry, variance components and Toeplitz. The covariance structure converging to the best fit, as determined by Akaike's information criterion, will be used.

The Kenward-Roger approximation will be used to estimate the denominator degrees of freedom.

Additional sensitivity analyses on the primary endpoint may be performed. Such sensitivity analyses will be specified in the TSAP.

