7.3.4 Safety analyses

Standard safety analyses will be performed on the TS.

Safety analyses will be descriptive in nature and will be based on BI standards. No formal inferential analysis is planned.

Adverse events will be coded using the Medical Dictionary for Regulatory Activities (MedDRA). AEs occurring one day before the first intake of the double-blind treatment will be assigned to the 'screening period'. AEs occurring between the first intake of the double-blind treatment and seven days after the last intake of double-blind treatment will be assigned to 'double-blind treatment period' for evaluation. AEs occurring thereafter will be assigned to 'post-treatment period'.

Frequency of patients with AEs will be summarised by system organ class (SOC) and preferred term (PT). In addition, AEs by intensity, drug-related AEs, serious AEs, AESIs and hypoglycaemic events will also be summarised.

Descriptive statistics of laboratory values for the change from baseline will be provided. Frequency tables of changes with respect to the reference range between baseline and last value on treatment will also be presented.

Change from baseline will be summarised for vital signs.

Further details on the safety analysis will be specified in the TSAP.

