7.7 DETERMINATION OF SAMPLE SIZE

Based upon previous experience with empagliflozin [[U12-3817-01](#)], it is estimated that the difference of change from baseline in HbA_{1c} after 16 weeks of treatment between empagliflozin (10 mg or 25 mg) and placebo add-on to insulin is 0.5% and that the standard deviation of this difference is 1.0%. The Type I error for each hierarchical testing procedure to evaluate superiority of empagliflozin 10 mg against placebo followed by superiority of empagliflozin 25 mg against placebo, is assumed to be 5% (two-sided), while maintaining the overall probability of type I error at 0.05.

The number of analysed patients should be 86 per treatment arm to have 90% power to test the primary endpoint of each empagliflozin 10 mg and 25 mg, leading to 81% overall power. Assuming that approximately 3% of patients will not be eligible for inclusion into the FAS, 3 additional patients should be randomised per arm. As such sample size will be 89 per arm. Calculations were performed using nQuery Advisor® 7.0.

Meanwhile, the draft version of the revised Japanese guideline “Clinical Evaluation Guidelines for Antihyperglycemic Drugs” [[R15-2907](#)] requires at least 100 patients who are treated for 1 year with oral antihyperglycemic drug. Therefore, assuming a 20 % loss of

Proprietary confidential information © 2016 Boehringer Ingelheim International GmbH or one or more of its affiliated companies

randomised patients during the 52 weeks of treatment, at least 63 patients should be randomised per arm (126 patients from both empagliflozin 10 mg and 25 mg arms).

On the basis of the above, a total of 267 patients (89 per arm) need to be randomised.

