## **7.2 CONCOMITANT DISEASES AND MEDICATION**

Only descriptive statistics are planned for this section of the report using the FAS. Concomitant medication use will be summarised by WHO Anatomical-Therapeutic-Chemical classification level 3 (ATC3) and preferred name. Summaries will be presented for concomitant therapies taken during randomised treatment and those taken at baseline. Separate summaries of use of antihypertensives, ASA or lipid lowering drugs at baseline by preferred name will be presented.

Prescribed background medication daily dose at baseline will be presented for total daily insulin.

Concomitant diseases will be summarised by MedDRA system organ class and preferred term. Relevant diabetic medical history by treatment group will also be presented. Both summaries will be presented using the FAS.

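### The lipid and FFA repeated-measures models in SAP 7.8.6 use one baseline slope for all visits, where the protocol's HbA1c model lets the slope vary by visit; a small, inexpensive specification gap in a supportive analysis

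*SAP*

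**What the plan says.** SAP 7.8.6 plans a separate MMRM for each lipid parameter and for FFA, on the treated set with values after rescue retained, "for both change from baseline at week 52 and percentage change from baseline at week 52 as dependent variables". The continuous covariates are given thus: "The MMRM models will include ‘baseline lipid’ (only for lipid parameters), ‘baseline FFA’ (only for FFA) and ‘baseline HbA1c’ as continuous covariates". The list of class effects (baseline eGFR, insulin type, treatment, visit) closes with "treatment by visit interaction’ as fixed effects". No term lets the baseline slope differ by visit, and no term represents lipid-lowering drugs.

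The protocol's HbA1c MMRM (7.3.1, a sensitivity analysis of the primary endpoint) has the same general form, but its model equation ends with "baseline HbA_{1c} by visit interaction + random error".

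On lipid-lowering drugs, SAP 7.2 says: "Separate summaries of use of antihypertensives, ASA or lipid lowering drugs at baseline by preferred name will be presented". So the drug data are collected, although 7.2 tabulates them on the full analysis set and the public text defines no yes/no flag.

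On status, protocol 7.3.4 says of the safety analyses: "No formal inferential analysis is planned". The lipids are listed among the safety laboratory parameters in protocol 5.3.3.

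**The concern.** In a model of change from baseline, the slope on baseline measures how far patients regress towards the mean by a given visit. If a later value is less closely related to baseline than an early one, the slope is steeper at the later visit. A common slope is a weighted average over visits, and in the scenarios below the early visits dominate it. It then corrects too little at week 52, the visit that SAP 7.8.6 names for these models. The arm that happens to start higher will seem to fall somewhat more than it should.

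At stake is the accuracy, in the one trial that is run, of the modelled week-52 lipid and FFA comparisons with placebo, and a little of their precision. The same trial allows visit-specific slopes for HbA1c, and the public SAP text gives no reason for a more restrictive form here.

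A lesser question is whether lipid-lowering drug use at baseline should be in the lipid models. Users and non-users regress towards different means, and a single baseline value captures that only in part.

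**Working it through.** **What the documents supply.** The only design figures concern HbA1c at week 16: 86 analysed per arm, 86/0.97 = 88.7, so 89 randomised; 0.9 × 0.9 = 0.81 overall power (protocol 7.7). These reproduce but do not bear on lipids. No lipid SD, correlation, slope or rate of drug use is given, so every lipid input below is an assumption. Two figures carry over: 89 per arm, and 20% loss over 52 weeks, which leaves 89 × 0.8 = about 71 per arm.

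**Visits.** Protocol 5.3.3 and the flow chart restrict Visits 6, 7, 9, 11, 12, 14, 15, 17 and 18 to haematology and urinalysis. Full chemistry, including lipids, then falls at Visits 8, 10, 13, 16 and 19: weeks 8, 16, 28, 40 and 52. FFA has its own row in the flow chart and was not computed separately.

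**Common slope.** Assume equal SDs at all visits, an unstructured covariance and complete data. Let r_j be the correlation of visit j with baseline.
- Slope of change on baseline at visit j: b_j = r_j − 1.
- Residual covariance: S_jk = ρ_jk − r_j r_k, with ρ_jk = 0.85 − 0.005 × weeks apart for different visits, and ρ_jj = 1.
- GLS weights: w = S⁻¹1 / (1ᵀS⁻¹1). Common slope: b = Σ w_j b_j.
- Share of a baseline gap left at week 52: |b_52 − b|.

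Let r fall linearly from 0.75 at week 8 to the week-52 value shown:

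| r at week 52 | Slope at week 52 | Common slope | Weight on weeks 8 and 16 | Share left |
|---|---|---|---|---|
| 0.75 (constant) | −0.25 | −0.25 | 44% | 0 |
| 0.65 | −0.35 | −0.289 | 56% | 6% |
| 0.55 | −0.45 | −0.308 | 67% | 14% |
| 0.45 | −0.55 | −0.306 | 78% | 24% |

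In the third row the weights are 0.435, 0.232, 0.114, 0.088 and 0.131 on slopes −0.250, −0.286, −0.341, −0.395 and −0.450. Their weighted sum is −0.308, and 0.450 − 0.308 = 0.142.

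**Size against the standard error.** With common SD σ, a one-standard-error baseline gap is σ√(2/89). The week-52 contrast has standard error of about σ√(1 − r²)√(2/71). So the shift as a fraction of that standard error is share × √(71/89) / √(1 − r²), free of σ:
- r = 0.65: 0.061 × 0.893 / 0.760 = 0.07
- r = 0.55: 0.142 × 0.893 / 0.835 = 0.15
- r = 0.45: 0.244 × 0.893 / 0.893 = 0.24

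**Precision, by simulation.**
- Same correlations, 89 per arm with 20% loss, 1,500 trials: the common slope multiplies the variance of the week-52 contrast by 1.00, 1.02 and 1.05 in the three declining scenarios.
- A different set-up (71 per arm, five visits, complete data, residual correlation 0.7 or 0.9 between adjacent visits, 4,000 runs per setting):

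| Slopes, first to last visit | Share left | SD, common / visit-specific |
|---|---|---|
| −0.4 throughout | 0 | 0.997 to 0.999 |
| −0.3 to −0.5 | about 0.10 | 1.006 to 1.009 |
| −0.2 to −0.6 | about 0.21 | 1.030 to 1.035 |

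In the second set-up, the mean error over randomisations was about zero throughout.

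**Lipid-lowering drugs (LDL, assumed).** A proportion p = 0.3-0.5 are users, whose values are d = 20-40 mg/dL lower at baseline and follow-up; within-group SD s = 28, within-group correlation r = 0.5-0.7. Put q = p(1 − p)d², V = s² + q and C = r s² + q. Residual variance given baseline is V − C²/V without the drug term and s²(1 − r²) with it.
- p = 0.3, d = 20, r = 0.7: V = 868, C = 632.8; 406.7 / 399.8 = 1.017.
- p = 0.5, d = 40, r = 0.5: V = 1184, C = 792; 654.2 / 588 = 1.113.

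The variance without the term is thus about 2-11% larger. Square roots 1.009 and 1.055 put the standard error about 1-5% larger. This already conditions on baseline lipid.

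**The case against.** The strongest reply is that this is a discretionary choice in a supportive analysis. Protocol 7.3.4 makes the safety analyses descriptive, no hypothesis or precision target attaches to lipids, and nothing requires a safety model to copy a sensitivity analysis of the primary endpoint. That stands, and it limits the weight of the point. It is not a reason to prefer the more restrictive model when the alternative costs almost nothing.

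The reply also says that the upper figures need a steep fall. If the correlation with baseline falls by the same 0.005 per week assumed between post-baseline visits, the share left is about 16% (0.75 at week 8, 0.53 at week 52), not 24%. That is fair: 24% is the end of an assumed range, not an expected value.

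Stronger readings are tempting, but the documents do not support them:
- *The lipid models lack baseline adjustment.* They do not: the baseline value of the analysed parameter is a covariate and removes most of any imbalance. In the table the common slope removes 0.289/0.35 = 83% down to 0.306/0.55 = 56% of what unadjusted change would carry.
- *Some of any baseline imbalance always remains.* Only if the slope changes across visits.
- *The week-52 contrasts are biased.* Not in expectation; the issue is a chance imbalance in one realised trial.
- *Week 52 is the only visit reported, or these are the only modelled lipid comparisons.* SAP 7.8.6 also gives descriptive statistics over time, and parts of the SAP are absent from the public text, so neither can be established.
- *Leaving out lipid-lowering drugs is an error.* It is a choice of prognostic covariate. Baseline lipid already carries part of that information, and nothing in the documents is contradicted.

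**Conclusion.** The point holds as a minor specification gap. SAP 7.8.6 assumes one baseline slope over 52 weeks, unlike the HbA1c MMRM in protocol 7.3.1. If the slope drifts, about 6-24% of a chance baseline difference may stay in the week-52 contrast, and its variance may be 0-5% larger. If the slope is constant, nothing is carried over and no precision is lost.

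These sizes rest on assumed correlations, equal SDs and the five-visit lipid schedule, and were worked for absolute change. Percentage change and FFA were not computed separately. No conclusion of the trial is shown to change, and the primary and secondary endpoints are untouched. The case for acting is the asymmetry: visit-specific slopes cost essentially nothing if they are not needed and remove the carry-over if they are.

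**What to change.** In SAP 7.8.6, add a baseline lipid by visit interaction to each lipid MMRM, and baseline FFA by visit to the FFA model, in line with protocol 7.3.1.

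Optionally, define a yes/no flag for lipid-lowering drug use at baseline on the treated set, from the concomitant therapy data already collected. Include it as a fixed effect in the lipid models, or pre-specify it as a sensitivity analysis.

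The cost is a line or two of SAP text and a few degrees of freedom among about 267 patients. With five lipid visits, the interaction uses four extra parameters per model and the drug flag one. No new data are needed.
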